## 5.6.2. Phase III

### 5.6.2.1. End of Treatment and Follow-up

End of treatment (EOT) is defined as the last planned administration or discontinuation of IMP for other reasons.

The FUV is scheduled to occur 28 days (if patient has been discharged) and 60 days after the randomization date. The visit information obtained at a site visit or via telephone call (e.g., AEs, survival status, according to the SoA, Table 2) should be recorded.

Discontinuation of study treatment does not represent withdrawal from the study.

For details on treatment discontinuation criteria, see Section 7.2.4.

### 5.6.2.2. End of Study

The end of study for the individual patient is defined as the date of the last contact of the follow-up period (i.e., 60 days after randomization), date of death, date of consent withdrawal from study participation (see Section 5.6.2.3), or the date of last contact when patients are lost to follow-up (see Section 5.6.2.4), whatever occurs earliest.

The entire study will end when all patients have discontinued IFX-1 AND all patients ended the study as described above.

The sponsor may prematurely terminate the study at any time earlier than planned for the following reasons:

- Unacceptable toxicity
- Administrative reasons

### 5.6.2.3. Consent Withdrawal/Discontinuation of Study Participation

A patient may withdraw from the entire study at any time at his/her own request without the need to provide any reason(s).

If the patient withdraws /patient is withdrawn by legal representatives/relatives from study participation, the sponsor may retain and continue to use any data collected before such a withdrawal of consent. However, in the case of deferred informed consent, if the consent is not obtained or if a legal representative denies the patient's participation in the study, the patient is excluded and data will no longer be used, except if local regulations would permit the use of such data in this situation (see Section 6.3). Patients (or legal representatives/relatives) who wish to withdraw consent/discontinue the study while still on treatment should be encouraged by the

investigator to perform the FUV for their own safety before any further data collection will be stopped.

If a patient (or legal representatives/relatives) withdraws from the study, he/she may request destruction of any samples taken and not tested, and the investigator must document this in the site study records.

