### Number of Patients:

**Phase II:** 30 patients (15 arm A+ 15 arm B)

**Phase III:** Total of 180 patients (approximately 90 per arm) in Stage 1 and 180 patients (approximately 90 per arm) in Stage 2 are planned. The assumed rate for randomization of additional patients, i.e. patients randomized in error (screening failures) and patients for whom consent is withdrawn within 48 hours after randomization, is 10%. The planned maximum number of patients in the study is 400, 200 patients per treatment arm. The sample size ensures 90% power to show superiority of IFX-1 for the primary endpoint of 28-day all-cause mortality. Sample size calculations were based on the assumption that IFX-1 can reduce a 30% mortality under SOC by 50% to a mortality of 15% and that at least 360 patients are evaluable for the primary endpoint for the final analysis.

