Phase III of the study will randomize up to 400 patients with one interim analysis for stopping for futility. A total of 180 patients are planned to be randomized into Arm A and Arm B using a 1:1 allocation ratio for the first stage; based on results of the interim analysis, up to an additional 180 patients are planned to be randomized using the same allocation ratio for the second stage. Additional patients will be randomized under the following conditions:

- For patients who were erroneously randomized (screening failures) and did not get IMP treatment.
- For patients who were randomized but consent was withdrawn (either by the patient or patient representative) within the first 48 hours after randomization, irrespective of whether IMP was administered or not.

The primary statistical analysis will be based on all randomized patients except patients randomized in error (reason for early termination documented as “Randomized by mistake” in the eCRF) who did not get IMP treatment.

In Phase III, patients will be treated with a maximum of 6 IV doses of IFX-1 800 mg (Arm A) or placebo (Arm B) at days 1, 2, 4, 8, 15, and 22, as long as the patient is still in the hospital (even if discharged from the ICU).

Patients will be assessed for quality of life using the EQ-5D.

Patients will be followed for survival and their clinical status assessed by the Glasgow Outcome Scale.

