#### 10.2.2. Analysis Sets

**Full analysis set (FAS):** The primary statistical analysis will be based on all randomized patients except patients randomized in error (reason for early termination documented as “Randomized by mistake” in the eCRF) who did not get IMP treatment.

**Safety analysis set (SAF):** Safety analyses will be based on all patients who received at least one infusion of IMP, and patients will be analyzed according to the treatment they actually received.

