#### **10.2.3.1. Primary Efficacy Analysis**

The primary analysis will be performed based on the FAS.

The primary efficacy variable is 28-day mortality (proportion of patients deceased until day 28). The primary statistical hypotheses to be tested are:

$H_0: HR = 1$

versus

$H_1: HR > 1$

where HR is the hazard ratio derived from the beta coefficient of the primary statistical analysis Cox regression model comparing the SOC + Placebo treatment arm (Arm B) with the SOC + IFX-1 treatment arm (Arm A).

A total of 180 patients are planned to be randomized to Arm A and Arm B using a 1:1 allocation ratio for the first stage. The interim analysis is performed after 180 patients, not counting patients being randomized in error, have been followed-up until day 28 (or died before). In case the interim analysis does not result in an early stop for futility, 180 additional patients are planned to be randomized in a ratio of 1:1 to Arm A and B. The planned maximum number of patients in the study is 360. Depending on the number of patients meeting criteria for additional randomization, more patients will be randomized but not more than 400.

The primary statistical analysis of IFX-1 + SOC compared to SOC alone will make use of a one-sided alpha level of 2.5% and will test for superiority (lower mortality among IFX-1 treated patients). The primary statistical analysis will be based on a Cox proportional hazards regression model with outcome 28-day all-cause mortality as a censored time-to-event variable and explanatory variables treatment arm (Arm B versus Arm A) and age. The primary statistical analysis will be based on all randomized patients except patients randomized in error (reason for early termination documented as “Randomized by mistake” in the eCRF) who did not get IMP treatment.. For the primary analysis, all-cause mortality will be censored at day 28 for subjects who died after day 28 or who have more than 28 days follow-up alive.

The z-statistic for the interim and final analysis will be calculated as the proportion of the beta coefficient for the treatment arm effect and its standard error from the Cox proportional hazards

regression model. The study will be stopped for futility if the z-statistic for the first stage is 0 or lower.

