#### **10.2.3.5. Interim Analysis**

The interim analysis is performed after the first 180 patients, not counting patients being randomized in error, in Stage 1 have been followed-up until day 28 (or died before). The study will be stopped for futility if the z-statistic of the primary efficacy analysis is 0 or lower. If the study is not stopped for futility, another up to 180 patients will be randomized in Stage 2. Depending on the number of patients meeting criteria for additional randomization, more than 360 patients will be randomized but not more than a total of 400.

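### Section 5.6.2.3 excludes deferred-consent patients whose consent is never obtained, including those who die first, while the FAS keeps them; the plan does not say which rule governs the mortality analysis

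*Combined protocol and SAP*

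**What the plan says.** All references are to protocol Version 4.0, Phase III.

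- **Section 5.6.2.3.** For deferred consent, the trigger is "if the consent is not obtained or if a legal representative denies" participation. The consequence is that "the patient is excluded and data will no longer be used, except if local regulations would permit the use of such data". Exclusion is the default and permission under local regulations is the exception, so on the text a country whose regulations are silent also excludes. The section points to Section 6.3.
- **Section 6.3.** It describes how consent is sought. It does not say what happens to the data when consent is never obtained, or which countries permit use.
- **Section 10.2.2.** For the FAS: "The primary statistical analysis will be based on all randomized patients except patients randomized in error" and not treated with IMP. The synopsis, Section 5.1 and Section 10.2.3.1 repeat this, and Section 10.2.3.1 adds: "The primary analysis will be performed based on the FAS". For the safety set (SAF): "Safety analyses will be based on all patients who received at least one infusion of IMP". Neither set has a consent-related exception.
- **Section 10.2.3.5.** "The interim analysis is performed after the first 180 patients, not counting patients being randomized in error", have reached day 28 or died.
- **Section 5.1.** "Additional patients will be randomized under the following conditions": randomization in error without IMP, and consent withdrawn by the patient or representative within 48 hours. The synopsis assumes that "at least 360 patients are evaluable for the primary endpoint for the final analysis" and allows about 10% extra randomizations, up to 400.
- **Section 10.2.3.** A separate Phase III SAP is to give exact definitions and the handling of missing and unused data. It is not part of the reviewed text.

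**The concern.** Two sections of one protocol answer the same question differently: is a randomized, treated patient whose consent was never obtained in the primary analysis? Section 10.2.2 says yes. Section 5.6.2.3 says no, unless local regulations permit use.

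The difference matters because of how a patient comes to have no consent. Refusal is a decision. Death before anyone entitled has signed is the primary endpoint itself. Since Section 5.6.2.3 puts both under one phrase, a patient who dies early without a signature can be removed, while a similar patient who lives long enough to consent stays. Exclusion then depends on the outcome being compared, which is what an all-randomized analysis set is meant to prevent.

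At stake are the definition of the primary population, the number of deaths available to the Cox model, the reported mortality in each arm, and a reader's ability to tell whether exclusions were balanced.

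**Working it through.** **1. The rules side by side.** Take a treated patient, not randomized in error, who dies before any entitled person consents.

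| Rule | Local regulations permit use | They do not |
|---|---|---|
| Section 5.6.2.3 | kept | excluded, data not used |
| FAS, Section 10.2.2 | kept | kept |
| SAF, Section 10.2.2 | kept | kept |
| Count of 180, Section 10.2.3.5 | counted (died) | counted (died) |
| Replacement, Section 5.1 | not triggered | not triggered |

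The rules agree in the middle column and conflict in the right-hand one. For a patient excluded alive before day 28 the interim count is unclear, because day-28 follow-up or death is also required. An early denial by a representative is arguably covered by the 48-hour replacement rule. A death before consent is not.

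**2. The plan's own figure.** Inputs from Section 10.2.1 and the synopsis: 180 per arm, 30% versus 15% mortality, one-sided 2.5%, 90% power. A two-proportion calculation gives 91.0% with continuity correction and 91.5% by Fisher's exact test, so the stated 90% reproduces and is not in dispute. For the planned time-to-event analysis:

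- Expected deaths: 180 × 0.30 + 180 × 0.15 = 54 + 27 = 81.
- HR (Arm B versus Arm A) = ln(0.70)/ln(0.85) = 2.195, and ln HR = 0.786.
- Schoenfeld power = Φ(√81/2 × 0.786 − 1.96) = Φ(1.577) = 94.3%.

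**3. Equal proportional loss.** The documents give no rate of consent never obtained, so the number of deaths removed, k, is an assumption and is varied. Let s = k/81. Deaths become 54(1 − s) and 27(1 − s); denominators become 180 − 54s and 180 − 27s; mB and mA are the resulting mortalities; HR = ln(1 − mB)/ln(1 − mA); power = Φ(√(81 − k)/2 × ln HR − 1.96).

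| k | Evaluable | Observed mortality, B vs A | HR | Schoenfeld power | Log-rank simulation |
|---|---|---|---|---|---|
| 0 | 360 | 30.0% vs 15.0% | 2.195 | 94.3% | 93.3% |
| 4 | 356 | 28.9% vs 14.4% | 2.204 | 93.4% | 92.4% |
| 8 | 352 | 27.9% vs 13.7% | 2.213 | 92.4% | 91.1% |
| 12 | 348 | 26.7% vs 13.1% | 2.222 | 91.3% | 90.2% |
| 16 | 344 | 25.6% vs 12.4% | 2.232 | 89.9% | 88.9% |

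At k = 16: √65/2 × 0.803 − 1.96 = 1.276, and Φ(1.276) = 89.9%. At k = 15 it is 90.3%. The simulation used 40,000 trials per row, exponential deaths to day 28 and an unadjusted test; it crosses 90% at about 13 deaths. The crossing depends on the method: continuity-corrected two-proportion power starts at 91.0% and is 89.8% at k = 4.

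Equal loss therefore hardly moves the HR. It costs events and understates mortality in both arms.

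**4. Strict null.** With 30% mortality in both arms and 10%, 20% or 40% of deaths removed with the same probability in each, the simulated one-sided rejection rate stays at 2.5%.

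**The case against.** The case for leaving this alone has real force.

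- **Blinding.** Phase III is double-blind and placebo-controlled (Section 5.1.2). Apart from emergency unblinding, consent-seeking cannot follow the arm. This stands: under a strict null the loss is equal in expectation. A reader might infer an inflated false-positive rate, but that needs unequal removal under the null, and the documents give no mechanism for it. What remains is that a treatment effect on early death could change who lives to consent, in a direction that cannot be fixed in advance.
- **Exposure.** Deferred consent is named for the Netherlands and Germany, plus unspecified country rules, in a trial of about 10 countries. Relatives or a representative may consent in the Netherlands, and a representative may sign in Germany. This stands. A reader might infer many exclusions because Section 6.3 expects a large proportion unable to consent beforehand, but that says nothing about how many never have consent obtained.
- **Fragility.** With 54/180 placebo deaths, 38/180 on IFX-1 gives z = 1.93 and 37/179 gives z = 2.02, so one dropped death could decide a boundary result. That is true of any exclusion and is not evidence about this rule.
- **The SAP.** It may settle the matter. It would then be settling a conflict that two protocol sections leave open.
- **Ethics.** Exclusion by default protects people who never consented. Reversing it is a policy change, not a clarification. This stands, and it limits the remedy.

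**Conclusion.** The conflict is real and can be read off the current text: Sections 5.6.2.3 and 10.2.2 define different primary analysis sets wherever local regulations do not permit use of the data, and no supplied section says which prevails. Because death before consent is not separated from refusal, following Section 5.6.2.3 links exclusion to 28-day mortality.

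The demonstrated size is modest. The number of patients affected cannot be derived and may be nil. The main expected effects are lost events and understated mortality in both arms. Schoenfeld power stays above 90% until about 16 of 81 expected deaths are lost, assuming the planned 30% and 15% mortality and the same proportion of deaths lost in each arm; other methods cross 90% earlier. Unequal loss is possible if treatment alters early deaths, but the documents support neither a size nor a direction. They do not support a claim that the trial is biased towards IFX-1, that type I error is inflated, or that power is inadequate. The point should be fixed before unblinding because the primary population is undefined for these patients, and a later choice could be questioned as data-driven.

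**What to change.** - In Section 5.6.2.3, separate (a) refusal or denial from (b) consent not obtained because of death or lasting incapacity.
- In Section 10.2.2, state that group (b) stays in the FAS with day-28 vital status wherever local regulations and the IRB/IEC permit. Settle this per country before unblinding, and say openly that it changes the current default and needs approval.
- State one rule for the FAS, the SAF and the interim count of 180.
- Report consent-related exclusions by arm.
- Add a sensitivity analysis that counts excluded patients known to have died by day 28 as deaths, where using that fact is lawful. Otherwise give a bounding analysis on the number excluded per arm.

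Cost: a protocol amendment with IRB/IEC approval (Appendix 2), a country-level legal check on data use, and one extra analysis; no added visits. The protocol does not itself establish a right to use vital status for excluded patients, so in some countries only the bounding analysis may be possible. Countries whose law bars use keep their exclusion.

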#### **5.6.2.4. Lost to Follow-up**

A patient will be considered lost to follow-up if he or she cannot be reached after hospital discharge for scheduled contacts and the study site is unable to make contact as described below.

The following actions must be taken if a patient cannot be reached:

- The site must attempt to re-contact the patient as soon as possible after the failed first scheduled contact.
- Before a patient is deemed lost to follow-up, the investigator or designee must make every effort to regain contact with the patient (where possible, 3 telephone calls and, if necessary, a certified letter to the patient's last known mailing address or local equivalent methods). These contact attempts should be documented in the patient's medical record.
- Should the patient continue to be unreachable, he/she will be considered to have withdrawn from the study with a primary reason of lost to follow-up.

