### 9.3. Death Reporting

The site should follow all patients for survival and collect information around the death on the appropriate eCRF form until the end of the study.

Primary cause of death should be reported in AE section and SAE form, as well as appropriate eCRF section(s). If symptoms of disease progression occurred and constitute the primary cause of death, these symptoms could be reported as fatal (S)AE (see Section 9.2.2).

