### 10.2. Phase III

#### 10.2.1. Sample Size Determination

A total of 180 patients (90 per arm) are planned to be randomized in Stage 1 and up to 180 patients (90 per arm) in Stage 2. For patients randomized in error (screening failures) and patients for whom consent is withdrawn within 48 hours after randomization, additional patients will be randomized. This results in 90% overall power to show efficacy in the final efficacy analysis. The power calculation is based on an overall 2.5% one-sided alpha and an assumed 30% 28-day mortality under Placebo and 15% 28-day mortality under IFX-1 treatment.

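### Withdrawal and loss to follow-up end a patient's participation with no stated route to vital status, while most of these patients stay in the mortality analyses

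*Combined protocol and SAP*

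**What the plan says.** All references are to protocol version 4.0, Phase III, unless stated.

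- **5.6.2.4** concerns patients who cannot be reached once they have left hospital. The site must try again promptly, telephone three times where it can and, if needed, send "a certified letter to the patient's last known mailing address or local equivalent methods". If that fails, "he/she will be considered to have withdrawn from the study with a primary reason of lost to follow-up".
- **5.6.2.2** takes the individual end of study as the earliest of several dates. These include the day consent is withdrawn "or the date of last contact when patients are lost to follow-up (see Section 5.6.2.4), whatever occurs earliest".
- **5.6.2.3** lets the sponsor keep data gathered before withdrawal. Patients who withdraw while on treatment should be encouraged by the "investigator to perform the FUV for their own safety before any further data collection will be stopped". If deferred consent is refused or never obtained, the patient is excluded and the data go unused unless local rules allow otherwise.
- **5.6.2.1** fixes the timing of that visit: "The FUV is scheduled to occur 28 days (if patient has been discharged) and 60 days after the randomization date".
- **9.3** reads: "The site should follow all patients for survival and collect information around the death", with the end of the study as the limit. Section 9 adds that deaths in follow-up and after the end of study are collected.
- **10.2.2** removes only untreated patients randomized in error from the FAS. Sections 10.2.3.1 and 10.2.3.2 analyse 28- and 60-day mortality on that set. The only censoring rule written out is administrative, at day 28. Section 10.2.3 leaves missing data to the SAP.
- The **Synopsis** allows 10% for additional randomization. This covers randomization errors and consent withdrawn within 48 hours, and nothing later.

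**The concern.** Death by day 28 is the primary endpoint. Death by day 60 is the first secondary endpoint, and four further tests depend on it. For both, the one fact needed from every FAS patient is whether he or she was alive on the day. That fact can often be learned after the patient stops answering the telephone or declines further visits, from a relative, a family doctor, another hospital or a register. The sections that govern withdrawal and loss ask for none of these.

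The instruction to withdrawing patients also does not fit the schedule. They are encouraged to complete a visit that is defined only at days 28 and 60, and no early-termination visit is described. A visit on, say, day 5 gives a date last known alive, but neither endpoint.

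At stake are endpoint data that could be obtained but are not collected. A later SAP rule can model missing vital status but cannot recover it. If the losses relate to outcome and differ by arm, the treatment comparison is exposed. The lost-to-follow-up text is the same in versions 2.0 and 4.0, although 60-day mortality rose in between from an other endpoint to the first secondary endpoint.

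**Working it through.** **Step 1. The passages side by side.**

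| Situation | Individual end of study | Route to later vital status in 5.6.2 | In the FAS? |
|---|---|---|---|
| Consent withdrawn | Withdrawal date (5.6.2.2) | None named | Yes (10.2.2) |
| Unreachable after discharge, repeated attempts failed | Last contact (5.6.2.2) | Attempts directed at the patient only | Yes (10.2.2) |
| Deferred consent refused or not obtained | Excluded, data unused unless local rules permit (5.6.2.3) | None | 10.2.2 does not remove them, so the two sections conflict |

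Section 9.3 extends survival follow-up to the end of the study but does not say whether this is the individual or the overall end. Section 9 mentions deaths after the end of study, but 9.1.1.1 and 9.1.2, which implement it, speak of SAEs related to study drug. A site cannot tell which passage governs.

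**Step 2. The plan's own power figure.** The inputs are from 10.2.1. The event rates are "an assumed 30% 28-day mortality under Placebo and 15% 28-day mortality under IFX-1 treatment". The test is one-sided at 0.025. With 180 per arm, the mean risk is 0.225 and the difference is 0.15.

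- Uncorrected: z = [0.15 × √180 − 1.96 × √(2 × 0.225 × 0.775)] / √(0.30 × 0.70 + 0.15 × 0.85) = (2.012 − 1.157) / 0.581 = 1.47, so power is 92.9%.
- Continuity-corrected: 180 per arm is equivalent to 166.9 uncorrected, so power is 91.0%. Fisher's exact test gives 91.5%.
- Cox model: 54 + 27 = 81 deaths and a hazard ratio of ln 0.85 / ln 0.70 = 0.456. Power is Φ(√(81/4) × |ln 0.456| − 1.96) = 94.3%.

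The stated 90% is reproduced by the corrected and exact calculations. The futility rule costs about 0.2 points.

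**Step 3. Power if vital status is missing unrelated to outcome.** The documents give no rate, so a range is assumed, with missing patients contributing nothing.

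| Unknown share | Known per arm | Corrected power | Uncorrected power |
|---|---|---|---|
| 5% | 171 | 89.5% | 91.7% |
| 10% | 162 | 87.7% | 90.2% |
| 15% | 153 | 85.6% | 88.5% |

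If 400 are randomized and 10% are unknown, 360 remain and power returns to 91.0% (corrected) or 92.9% (uncorrected). Power is not the main issue.

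**Step 4. Loss at random after discharge.** An illustrative simulation used 400,000 patients per arm. It assumed 28/60-day mortality of 30/36% on placebo and 15/20% on IFX-1, 45% and 60% of survivors discharged by day 28, and no deaths after discharge. A fraction of discharged patients was censored at discharge. None of the 60-day, discharge or loss figures is in the documents.

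| Lost among discharged | 60-day placebo | 60-day IFX-1 | Difference | ln(survival) ratio |
|---|---|---|---|---|
| 0% | 36.0% | 20.0% | 16.0 points | 0.50 |
| 10% | 36.5% | 20.6% | 15.9 points | 0.51 |
| 20% | 37.3% | 21.2% | 16.1 points | 0.51 |

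Each arm's mortality is slightly overstated, because those lost are healthier than those still at risk. The contrast hardly moves.

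**Step 5. Loss related to outcome.** If k of 180 patients per arm have unknown status, the risk difference can move by up to k/180 either way. For k = 9 that is 5 points. At the planned 27 versus 54 deaths the unadjusted z is 3.41. If 11 IFX-1 deaths (11/180 = 6.1% of the arm) had gone unseen, the true table would be 38 versus 54, with z = (0.3000 − 0.2111) / √(0.2556 × 0.7444 × 2/180) = 1.93, below 1.96. This is a stress case in one direction. It counts unknowns as survivors, whereas the planned Cox analysis would censor them.

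**The case against.** A reader might infer that one missed call ends all follow-up, vital status included. The text does not support that. Section 5.6.2.4 requires every effort: prompt re-contact, telephone calls, a letter and local equivalents. It also defines loss by scheduled contacts in the plural, so the view that a failed day 28 contact cancels day 60 is one reading and not a stated rule. Sections 9 and 9.3 point towards continued collection of deaths, and a site that learns of a death would have to record it. The accurate description is an unreconciled gap, not a plain end to survival follow-up.

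Other strong readings also fail:

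- **Forty patients and nine unseen deaths.** The products 10% × 400 = 40 and 40 × 22.5% = 9 are ceilings. The allowance is shared with randomization errors, refused deferred consent leads to exclusion, and the figure says nothing about loss after discharge.
- **Early visits entered on day 28 or day 60 forms.** The case report form is not among the documents, so this cannot be known. Consent pages are not available either, so nothing can be said about what patients are asked there.
- **A demonstrated bias.** Step 4 shows almost none in the treatment contrast, and its unequal loss between arms comes entirely from assumed discharge rates.

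It is also fair that deaths in hospital by day 28 are seen directly, that stopping study drug is already separated from withdrawal, and that missing-data rules are left to the SAP. Two qualifications remain. Withdrawal in the ICU affects both endpoints. Section 7.2.4 foresees transfer to another hospital; if a site treats transfer as discharge, which the text does not settle, a patient still ventilated elsewhere could become unreachable.

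**Conclusion.** The point holds as a gap in the rules for collecting vital status. Sections 5.6.2.2 to 5.6.2.4 close a patient's participation at withdrawal or, after repeated failed attempts, at last contact. They name no third-party source and no survival-only withdrawal, and they are not aligned with sections 9, 9.3 and 10.2.2. Refused or unobtained deferred consent apart, the affected patients remain in the FAS for both mortality endpoints.

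Its size cannot be stated, because the documents give no rate for late withdrawal or loss. Under the assumed range, outcome-neutral loss of 5 to 10% leaves corrected power at 89.5 to 87.7%, against 91.0% with none, and random loss after discharge leaves the 60-day difference at about 16 points. The exposure is to informative loss, bounded only by the share with unknown status. Loss after discharge bears mainly on day 60, and withdrawal in the ICU on both days. The gain from a change is more complete endpoint data and protection against informative loss, not the correction of a proven bias. It is a cheap improvement worth making.

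**What to change.** - **5.6.2.4.** State that a failed day 28 contact does not end participation, that the day 60 contact is still attempted before a patient is declared lost, and that a patient known alive at day 60 counts as alive at day 28. Before that label is applied, seek vital status from next of kin or representative, family doctor, receiving hospital or a public register, where local law and consent permit.
- **5.6.2.3.** At withdrawal, record whether the patient or representative allows a vital-status check at days 28 and 60. Replace the instruction to complete the follow-up visit with an early-termination assessment, kept separate from the day 28 and day 60 visits.
- **5.6.2.2, 9.3 and 10.2.2.** Align them: say whether survival follow-up runs to the individual or the overall end of study, and how the FAS treats patients excluded for want of deferred consent.
- **SAP.** Specify in advance the handling of unknown vital status at days 28 and 60, with a sensitivity analysis.

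The cost is protocol and consent wording, one case report form page and a few extra contacts. Some countries restrict register checks, so the wording must be conditional on local permission.
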